3. ORGANISATION	
Data Monitoring Committee	8
Steering Committee	8
Substudy Protocol Committee	8
Co-ordinating Centre responsibilities	8
Publication	8
Financial support	ð o
	8
4. REFERENCES	9
APPENDICES	
1 Participating hospitals	10
2 Investigator CT scan form	11
3a Legal Representative information & consent	12
3b Patient information & consent	15

CRASH-2 substudy

The effect of tranexamic acid on intracranial bleeding among CRASH-2 trial participants

1. Background

CRASH-2 is a large randomised controlled trial of the effect on mortality and transfusion requirements of tranexamic acid (TXA) in trauma patients with significant bleeding (www.crash2.Lshtm.ac.uk). Over 9,000 patients have been enrolled so far and recruitment will continue until 20,000 patients have been randomised. Many of the patients included in the CRASH-2 trial have multiple injuries and in about 40% of patients this includes traumatic brain injury (TBI). The CRASH-2 trial will assess as sub-group analyses, the effect of TXA in patients who also have TBI. These analyses will examine the effect of TXA on mortality, on the need for a neurosurgical operation and on neurological impairment, using a modified version of the Oxford Handicap Score (our previous analyses have shown that this score is strongly correlated with outcome on the Glasgow Outcome Scale at six months).

Traumatic intracranial bleeding: TBI is commonly accompanied by intracranial bleeding, which can be epidural, subdural, subarachnoid or parenchymal. Of the 7,814 patients with TBI enrolled in the MRC CRASH trial who had a computerised tomography (CT) scan, 31% had subarachnoid haemorrhage and 40% had an intracranial haematoma. Overall 56% of TBI patients had some type of intracranial bleeding.¹

Prognostic studies show that intracranial bleeding is associated with increased mortality and disability six months after injury. In the MRC CRASH trial, the presence of subarachnoid haemorrhage, petechial haemorrhage or intracranial haematoma were independently associated with poor outcome at 2 weeks and 6 months.² Similarly, the IMPACT study found that after controlling for age, Glasgow Coma Score (GCS) motor score and pupil reactions, subarachnoid and subdural haemorrhages more than doubled the odds of poor outcome at six months.³ The larger the intracranial bleeding, wherever the location, the worse prognosis it is associated with. The Brain Trauma Foundation Guideline for Surgery takes into account the bleeding size to recommend surgical

evacuation: 50 cm³ for parenchymal haematoma, 30 cm³ for epidural and 10 mm for subdural haematoma.⁵

In patients with TBI, intracranial bleeding can develop or worsen after hospital admission. Studies involving repeated CT scanning have found that intracranial bleeds can develop or expand in the 24 hours after injury. Ortel studied a group of patients in whom two CT scans were obtained within 24 hours of injury to determine the prevalence of progressive intracranial haemorrhage.⁴ Among patients who had their first CT scan within 2 hours of injury, 49% had radiological evidence of progressive haemorrhage. Yadav conducted repeat CT scanning of TBI patients at hospital admission and 24 hours later, and found that 16% of 262 parenchymal haematomas and contusions increased in size in the first 24 hours.⁶ Similarly, Sullivan et al found that traumatic epidural haemorrhages enlarged in 23% of 160 TBI patients treated non-operatively.⁷ The mean enlargement was 7 mm, and the mean time to enlargement was 8 hours from injury and 5.3 hours from CT diagnosis. Although these studies provide estimates of the occurrence of intracranial bleeding and expansion they all have limitations. All included patients who have an abnormal initial CT scan and there is little information on the proportion of patients that develop new intracranial bleeds in the first 24 hours who have the potential to benefit from early treatment.

Tranexamic acid and intracranial bleeding: Tranexamic acid is commonly used in surgery to reduce blood loss. A systematic review of randomised controlled trials of TXA in elective surgery showed that it reduces the need for transfusion by one third, reduces donor exposure by one unit, and halves the need for further surgery to control bleeding.⁸ A systematic review of randomised trials of TXA in patients with aneurismal subarachnoid haemorrhage showed that TXA reduced the rate of re-bleeding by approximately 40%, but because of an increase in cerebral ischaemia there was no overall benefit.⁹ However, the duration of TXA treatment in these trials was six weeks and it is possible that a shorter treatment might prevent re-bleeding whilst avoiding the risk of ischaemia. The systematic review was conducted in 2003 but since then a randomised controlled trial of the early administration of a short course (3 days) of TXA in aneurysmal subarachnoid haemorrhage found that TXA reduced the occurrence of re-bleeding from 10.8% to 2.4% with no evidence of increased side effects.¹⁰ Almost all of the effect on re-bleeding was observed within the first few hours after hospital admission. Tranexamic acid could also improve outcome after TBI by reducing systemic blood loss. Hypotension is an established risk factor for poor outcome after TBI.

Hypothesis: Early administration of TXA can prevent the occurrence or increase of intracranial bleeding in patients with TBI and significant bleeding.

Aim: The aim of the proposed substudy is to quantify the effect on intracranial bleeding of the early administration of TXA, in CRASH-2 trial participants with traumatic brain injury.

Primary outcome:

1) Increase in volume of intracranial bleeding

Secondary outcomes:

- 1) Frequency of progressive haematomas
- 2) Frequency of delayed haematomas
- 3) New focal ischaemic lesions

Other relevant outcomes including mortality, disability, need of neurosurgical operation and non fatal thromboembolic events are collected in the CRASH-2 trial and will be reported for the TBI subgroup in the main analysis.

2. Study design

Methods

Participating hospitals: Participating hospitals have been selected based on level of interest by the principal investigator in the research question, the recruitment rate in the CRASH-2 trial and the ability of the hospital to collect and send the necessary CT scan data to the trial co-ordinating centre. This substudy will be conducted in the hospitals listed in Appendix 1.

Inclusion criteria: All patients meeting the following criteria will be eligible for inclusion in the substudy:

- Fulfils the inclusion criteria for the CRASH-2 trial
- GCS of 14 or less
- Baseline clinical CT scan shows intracranial abnormality consistent with TBI
- Non pregnant

Version date:12/06/2008

Number of patients needed: Assuming a baseline intracranial bleeding volume of 20 ml, an average increase of 7 ml in the control group and a correlation of 0.6 between baseline and follow-up bleeding, we need to recruit 900 patients to have 80% power (with alpha=0.05) to detect a 20% reduction in the increase of intracranial bleeding volume in the control group. If 400 patients were recruited the trial could detect a 30% reduction in the primary outcome. A sample size of 200 patients could detect a 40% reduction in the primary outcome.

Procedures: Patients will follow all procedures as per CRASH-2 protocol; Additional procedures for the substudy are as follows:

Patients enrolled in the substudy will be identified by the completion of one form that will collect data on time since injury, time of initial (pre-randomisation) and follow-up CT scans and the file identifiers of the respective CT scan images. This form will also collect information on whether or not a decision to undertake neurosurgery was taken based on the CT scan result (see Appendix 2). This form will be sent to the trial co-ordinating centre in the same way as the CRASH-2 trial data.

CT scan protocol:

CT scan data acquisition: Two CT scans will be obtained for each participant, a clinical pre-randomisation scan and second scan 24-48 hours later. CT scans will be sent to the co-ordinating centre by uploading them onto the CRASH-2 trial server. Scans will be checked by the trial data manager to ensure that they are of the head, from the correct patient, performed on the correct date and of sufficient quality to be read. All study sites will be required to provide documentation as to the standard parameters used for each CT scanner. The specific scan protocol/parameters of the initial CT evaluation will be limited by the emergent nature at the time of admission. However, after a patient is enrolled, the follow-up scan must match the baseline CT scan with regard to section thickness, section spacing (overlap or no gap), matrix, field of view, and scan angulations. Consistency in these parameters across all CT evaluations for a patient allow comparable measurements because of identical spatial resolution. All name identifiers will be removed before loading the scans onto the CT reading system. The CT scans will be allocated to an expert CT scan reader for evaluation who will be blind to the treatment allocation.

CT scan data analysis: In both CT scans we will measure: type of bleeding (subdural, epidural, subarachnoid haemorrhage, parenchymal haematoma) volume of bleeding, ischaemic lesions and indirect signs of intracranial pressure. Volume of intracranial bleeding will be measured using validated methods; further details are described in the statistical analysis plan.

Consent

Because patients included in this substudy will have significant TBI, relatives or legal representatives would be asked to sign the informed consent in line with local legal requirements. To minimise the need for multiple information sheets and consent forms, one form which combines the CRASH-2 and substudy information will be used (Appendix 3).

Randomisation

As per CRASH-2 protocol

Treatment As per CRASH-2 protocol

Serious unexpected suspected adverse events As per CRASH-2 protocol

Expected side effects As per CRASH-2 protocol

Potential risks associated with this substudy

It is standard care for all patients with a history of TBI and associated clinical signs to have a CT scan. Therefore, the initial scan will form part of standard care. The substudy requires one additional CT Scan to be done 24 to 48 hours after the first, which in many cases is likely to be clinically indicated. The effective radiation dose from a CT scan is about 2 mSv, which is about the amount received from background radiation in eight months.

Unblinding

As per CRASH-2 protocol

Analysis

Haemorrhage volume from CT scans will be analysed with use of generalised linear mixed models. The baseline bleeding volume and the time from injury to CT will be included as covariates. Because patients who undergo a neurosurgery based on the pre-randomisation CT scan would not have a baseline haematoma they would be excluded of this analysis.

We will express the effect of TXA on the occurrence of secondary endpoints using relative risks and 95% confidence intervals. All analysis will be based on the intention to treat principle. We will conduct subgroup analysis according to type of bleeding. No interim analysis is planned for the sub-study; the analysis will be done at the end of the CRASH-2 Trial. Further details are described in the statistical analysis plan.

Definitions

Progressive haematoma will be defined as a growth of the haematoma larger than 25% from the initial to the follow-up CT scan.

Delayed haematoma will be defined as appearance of an haematoma in the follow-up CT scan where there was not one on the initial scan.

New focal ischaemic lesions will be defined as those ischaemic lesions which appear in the follow-up CT scan but not in the initial one.

3. Organisation

Data monitoring committee

The data monitoring committee members would be the same as CRASH-2. Standard Operating Procedures: As per CRASH-2 protocol

Steering committee

The steering committee members would be the same as CRASH-2 plus [name]. Standard Operating Procedures: As per CRASH-2 protocol

Substudy Protocol Committee

[name] (UK), [name] (India), [name] (India), [name] (Colombia), [name] (UK), [name] (UK), [name] (India), [name] (India), [name] (UK), [name] (UK), [name] (UK), [name] (UK)

Co-ordinating centre responsibilities

As per CRASH-2 protocol

Publication

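### The 200-patient figure for a 40% reduction is slightly optimistic: the scaling that links 900 to 400 gives 225, and 200 patients give about 75% power

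*Protocol*

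**What the plan says.** Protocol, section 2 (Study design), paragraph on the number of patients needed. The assumptions are listed once: "Assuming a baseline intracranial bleeding volume of 20 ml", then "an average increase of 7 ml in the control group and a correlation of 0.6 between baseline and follow-up bleeding". The main requirement follows: "we need to recruit 900 patients to have 80% power (with alpha=0.05", for a 20% reduction in the control-group increase.

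Two further scenarios come directly after it. The first lowers the size to 400: "If 400 patients were recruited the trial could detect a 30% reduction in the primary outcome".

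The second, which is the one in question here, lowers it again: "A sample size of 200 patients could detect a 40% reduction in the primary outcome".

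Neither sentence brings in a new assumption, and neither repeats the power. The paragraph gives no standard deviation and no formula, and does not say whether alpha is one- or two-sided. The allocation ratio is left to the CRASH-2 protocol.

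**The concern.** Three sizes that share one set of assumptions should be linked by a simple rule. If only the effect to be detected changes, the required number falls with the square of that effect. The step from 20% to 30% obeys this rule exactly; the step to 40% does not.

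At stake is whether the third sentence is accurate. Someone who uses it to judge what 200 patients can show would take the power for a 40% reduction to be 80%, that is, a type II error of 20%. The arithmetic that fits the other two figures gives a type II error of about 25%.

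**Working it through.** **Inputs.** All are from the protocol paragraph unless marked as an assumption.

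- Control-group increase 7 ml, so reductions of 20%, 30% and 40% are differences of 1.4, 2.1 and 2.8 ml.
- Alpha 0.05. Two-sided is an assumption; one-sided is also shown.
- Power 80%, stated with the 900 and carried over here to 400 and 200. That is an inference.
- Standard deviation and allocation ratio: not given. They cancel in step 1, as does the correlation of 0.6.
- Constant variance across scenarios: an assumption, examined in step 4.

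**Step 1. Link the three sizes.** For a comparison of two means, total N = k / (effect)², where k holds alpha, power, residual variance and allocation. With k fixed:

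- 30%: 900 × (20/30)² = 400. This reproduces the stated figure exactly.
- 40%: 900 × (20/40)² = 225. The stated figure is 200.
- Starting from 400 at 30% instead: 400 × (30/40)² = 225 again.
- Starting from 200 at 40%: 200 × (40/20)² = 800 for 20%, and 200 × (40/30)² = 356 for 30%. Neither matches.

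Two figures agree and the third is the outlier. In whole, equal arms, 225 becomes 226.

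**Step 2. What 200 patients provide.** With two-sided alpha the normal quantiles sum to 1.960 + 0.842 = 2.8016 (from unrounded values).

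- Power for a 40% reduction: Φ(2.8016 × √(200/225) − 1.960) = Φ(0.681) = 75.2%. A t-based calculation gives 74.8%. One-sided alpha gives 75.8%.
- Reduction detectable with 80% power: 20% × √(900/200) = 42.4%.

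**Step 3. The same result as a residual SD.** Assuming two-sided alpha and 1:1 allocation, SD = difference / (2.8016 × √(4/N)):

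- 900 patients, 1.4 ml: 7.50 ml
- 400 patients, 2.1 ml: 7.50 ml
- 200 patients, 2.8 ml: 7.07 ml

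With one-sided alpha the first two become about 8.45 ml. The level depends on these assumptions; the mismatch does not.

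**Step 4. Could rounding or another variance model explain it?**

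Suppose 900 was itself rounded to the nearest hundred:

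| True N at 20% | N at 30% | N at 40% | Power at 200 for 40% |
|---|---|---|---|
| 850 | 378 | 213 | 77.6% |
| 900 | 400 | 225 | 75.2% |
| 950 | 422 | 238 | 72.9% |

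Under constant variance, 200 does not reach 80% power anywhere in this range.

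Other models, each started from 900 at 20%, with r the proportional reduction:

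| Model | N proportional to | N at 30% | N at 40% |
|---|---|---|---|
| Log ratio of the increase | 1 / [ln(1−r)]² | 352 | 172 |
| SD proportional to the increase | [1+(1−r)²] / r² | 363 | 187 |
| Variance proportional to the increase | (2−r) / r² | 378 | 200 |
| Log ratio of follow-up volume (27 ml in controls) | 1 / [ln((27−7r)/27)]² | 389 | 213 |
| SD proportional to follow-up volume | [27²+(27−7r)²] / r² | 390 | 214 |

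None gives both 400 and 200 before rounding. The model that gives 200 at 40% gives 378 at 30%.

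**The case against.** The best defence is rounding. All three sizes are whole hundreds and all three effects are whole tens of percent. To those units, 225 is 200 and 42.4% is 40%. Read as approximate, the paragraph is consistent: any first figure from 850 to 950 leads to sizes that round to 400 and 200, and so does every model in the second table. This probably explains how the figure arose. It does not make the sentence accurate, because rounding a required size down overstates what that size can detect.

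A second objection is that constant variance is the reviewer's choice. The protocol names no variance model, and its Analysis section plans generalised linear mixed models. Under three of the five alternatives, 200 would be enough for a 40% reduction. This stands as a limit on the point. Constant variance is still the simplest reading and the only one tried that gives the stated 400 exactly.

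Third, the sentence on 200 patients does not repeat the 80% power. That is true. Carrying it over is an inference, though the paragraph offers no other value.

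A reader might also infer that 200 is a fallback size on which the substudy would be judged, and that a null result at 200 would be misread. The documents do not support this. The paragraph does not call 200 a minimum or a threshold, and the only size the protocol says it needs is 900. No interim analysis is planned, and no stopping or interpretation rule uses 200. Moving the detectable reduction from 40% to about 42% would hardly change how an estimate and its confidence interval are read.

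**Conclusion.** The point holds as a minor arithmetic inconsistency. If 80% power and constant variance apply to all three scenarios, 225 patients are needed for a 40% reduction, 25 more than stated. Put the other way, 200 patients lose about 5 points of power (75% instead of 80%), or 2.4 percentage points of detectable reduction (42.4% instead of 40%). Allocation, correlation and the missing standard deviation do not affect the comparison, and the sidedness of alpha hardly does.

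The error concerns a secondary scenario. It does not show that 900 is wrong: that figure cannot be rebuilt here because the paragraph gives no standard deviation, and nothing in this check depends on doing so. Design and analysis are unaffected.

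**What to change.** Replace the last sentence of the sample size paragraph with one of these:

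- *200 patients could detect a 42% reduction with 80% power (about 75% power for a 40% reduction).*
- *About 225 patients could detect a 40% reduction.*

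Also state that 80% power applies to all three scenarios. If the original calculation used a variance model that does give 200, naming it would serve equally well, provided that the 400 is then checked against the same model.

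The cost is an edit to one paragraph. It needs no extra patients and no change to the design, the analysis or the target of 900.

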Appendix 2 - Investigator CT scan form

	completed after the in	nitial CT Scan		
. Hospital ID	v			
2. Patient initials	3. Patient hospital identification number	4. Box Pack		
5. CT scan compatible	6. Time and date of injury	7. Time and date of initial CT scan		
with head injury (circle the correct answer)	Time: (24 hours)	Time : (24 hours)		
Yes No	Date// (dd/mm/)	yy) Date/(dd/mm/yy)		
initial CT results? (circle the o	correct answer)	flick all that apply) arenchymal pidural Subdural		
9. CT scan Identifier:	10. CT scan parameters			
(OFFICE USE ONLY)	Section thickness:			
	Section spacing:			
	Matrix:			
	Eald af view			
	Field of view:			
	Scan angulations :	.a		

13. Patient initials	14. Patient hospital identification number		15. Box Pac	sk 🔤		
16. Time and date of fold	ow-up CT scan					
Time:	(24 hours)					
Date / /	(dd/mm/yy)					
17a. Haematoma evacu follow-up CT results? (circle	uation decided based on the correct answer!	17b. If yes, type of I	haematon	na evac (tic	cuate ck a8 #	ed: not opply
Yes No		Epidural Subdural				
18. CT scan identifier:	19. CT scan parameters		90			
(OFFICE USE ONLY)	Section thickness:					
	Section spacing:			1.1.1		
	Matrix:					
	Field of view:					
	Scan angulations:					
20. Name of the person completing the form		2	1. Date

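### Haematomas evacuated between the two scans are not covered by the surgical exclusion, so growth that led to surgery would be recorded as a fall in volume and dilute the TXA effect

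*Protocol*

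**What the plan says.** The primary outcome (Protocol, section 1) is "Increase in volume of intracranial bleeding". It is measured between two scans, described under CT scan data acquisition as "a clinical pre-randomisation scan and second scan 24-48 hours later".

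The Analysis paragraph in section 2 specifies generalised linear mixed models and adds: "The baseline bleeding volume and the time from injury to CT will be included as covariates". Its one rule on surgery is: "patients who undergo a neurosurgery based on the pre-randomisation CT scan would not have a baseline haematoma they would be excluded". It then states: "All analysis will be based on the intention to treat principle". Further detail is left to the SAP.

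Under Definitions: "Progressive haematoma will be defined as a growth of the haematoma larger than 25% from the initial to the follow-up CT scan".

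On data capture, the Procedures paragraph says that the substudy form records whether neurosurgery was decided on the CT result. The legible part of Appendix 2 asks about evacuation decided on the initial CT and, in item 17a, on the "follow-up CT results". No legible item covers an operation between the scans on other grounds, and none asks for the date or time of an operation. Section 1 notes that the need for a neurosurgical operation is collected in the main CRASH-2 trial and reported there.

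**The concern.** The exclusion is tied to one trigger, the pre-randomisation CT. A patient whose bleed expands after randomisation, and who is operated on after deteriorating or after an unscheduled scan, falls outside it. The volume at 24-48 hours is then what is left after surgery, so growth large enough to lead to an operation is recorded as shrinkage.

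The stated reason for the exclusion also does not fit. Patients operated on because of the pre-randomisation CT do have a haematoma on that scan. What they lack is an interpretable follow-up volume, and that is equally true of anyone evacuated before the second scan.

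The event is foreseeable from the protocol's own background, which reports epidural enlargement at a mean of 8 hours from injury, well before a 24-48 hour scan, and cites size thresholds for evacuation. Such surgery is a consequence of the outcome being measured. If TXA limits growth, more control than TXA patients are evacuated, and the misrecorded values narrow the difference between arms.

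**Working it through.** **Inputs from the protocol (Number of patients needed).** Baseline 20 ml; control increase 7 ml; baseline/follow-up correlation 0.6; 900 patients; 80% power; alpha 0.05; 20% reduction = 0.20 × 7 = 1.4 ml. Two-sided testing and 1:1 allocation are assumed.

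**Step 1: the plan's own figure.** No SD is given, so 900 cannot be reproduced independently, but it implies one. With 450 per arm:

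residual SD = 1.4 × √(450/2) / (1.960 + 0.842) = 1.4 × 15 / 2.802 = 7.50 ml.

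With baseline adjustment, raw SD = 7.50 / √(1 − 0.6²) = 7.50 / 0.8 = 9.37 ml. This also returns 400 patients for a 30% reduction. For 40% it gives 226 rather than 200, which does not bear on this point.

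Power = Φ(|estimate| / (s × √(4/900)) − 1.96). With no evacuation: 7.50 × 0.0667 = 0.50; 1.4 / 0.50 = 2.80; Φ(0.84) = 80%.

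**Step 2: add evacuation between scans.** Simulated follow-up volumes use the means, correlation and SD above. Three assumptions do not come from the documents: the share of controls evacuated; 5 ml left after surgery; and log-odds of evacuation rising 0.1 or 0.3 per ml of growth, with the same rule in both arms. Post-evacuation volumes are kept and follow-up is regressed on arm and baseline.

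| Controls evacuated | Estimate, slope 0.1 | Power | Estimate, slope 0.3 | Power |
|---|---|---|---|---|
| none | 1.4 ml | 80% | 1.4 ml | 80% |
| 2% | 1.3 ml | 71% | 1.2 ml | 67% |
| 5% | 1.2 ml | 56% | 1.0 ml | 50% |
| 10% | 1.0 ml | 38% | 0.7 ml | 24% |

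Repeat runs differ by up to about 0.05 ml and three percentage points. Worked example for the last cell: estimate 0.69 ml, residual SD 8.27 ml; 8.27 × 0.0667 = 0.551; 0.69 / 0.551 = 1.25; Φ(1.25 − 1.96) = Φ(−0.71) = 24%.

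**Step 3: how the patients are misrecorded.** With a sharp growth trigger and 1-10% of controls evacuated, patients who would have grown by 21-29 ml on average are recorded with a mean change of about 0 to −13 ml, depending on the volume left (0-10 ml).

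**Step 4: sensitivity to the cause of surgery.** If evacuation is unrelated to growth (5% evacuated, 5 ml left), the estimate stays near 1.3 ml and the loss is mainly power, to about 63%.

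The cited size thresholds give a second view. Under the plan's means and implied SD, 26% of controls and 22% of TXA patients cross 30 ml between scans. If one in five of those were evacuated to 5 ml, the estimate would be 1.10 ml with 48% power. Only 0.7% of controls cross 50 ml. Even if all of those in both arms were evacuated, the estimate would be 1.28 ml with 70% power.

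**Step 5: progressive haematoma.** In the same model 58.2% of controls and 52.4% of TXA patients grow by more than 25%: 52.4 / 58.2 = 0.90. If the fastest-growing 5% of controls, and the 3.5% of TXA patients above the same threshold, are scored not progressive: (52.4 − 3.5) / (58.2 − 5.0) = 48.9 / 53.2 = 0.92. At 2% and 10% the ratio is 0.91 and 0.93.

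**Step 6: does extending the exclusion solve it?** Not fully, because it conditions on a post-randomisation event that depends on the outcome. With a sharp growth trigger, excluding all evacuated patients leaves about 1.15-1.20 ml at 5% and 1.08 ml at 10%. With slope 0.3 it leaves roughly 1.2 ml.

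**The case against.** **The SAP may deal with this.** The Analysis section defers detail to a SAP that is not shown, and handling of post-randomisation surgery is often placed there. Nowhere does the protocol say outright that post-evacuation volumes count as growth; that follows from the single exclusion plus the intention-to-treat sentence. This stands as a limit on certainty. It does not remove the point: the protocol chose a surgical rule and drew it too narrowly, and a SAP cannot supply operation times that were never collected.

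**The patients may be identifiable.** A reader might infer that the analyst has no means of finding them. The documents do not support that. CRASH-2 collects the need for a neurosurgical operation; set against the two form items, this could flag patients operated on for neither scan, and the CT reader may see that a clot has been removed. But the visible text does not link the main-trial item to this analysis or show that surgery is timed against the scans.

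**The form is damaged.** The extracted text of Appendix 2 jumps from item 10 to item 13, so its full content cannot be confirmed. The Procedures paragraph, which limits the form to surgery decided on a CT result, supports the reading taken here.

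**The size is assumed.** At 1-2% of controls evacuated the estimate is still 1.2-1.3 ml, with 67-74% power. This objection stands in full.

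**Conclusion.** The gap is real. Followed as written, the plan reads a haematoma evacuated before the second scan as shrinkage and as not progressive. When growth drives surgery, the volume difference is diluted towards zero: modestly at 2% of controls evacuated, with serious loss of power at 5-10%. The effect on the progression relative risk is small.

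Two stronger readings are tempting and not supported. One is that a true TXA effect is certainly hidden: that describes the upper end of an assumed range, and the documents give no evacuation rate. The other is that the bias could reverse the sign. In the calculations that happened only in extreme cases: a near-threshold trigger (slope 1 per ml) with 25% of controls evacuated, or evacuation of every patient crossing 30 ml (26% of controls).

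The figures rest on the SD implied by 900 patients, near-normal volumes, 5 ml left after surgery in the main table, and the same evacuation rule in both arms. This should be fixed; confidence is moderate because the rate is unknown and the SAP is not shown.

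**What to change.** 1. Add one item to the investigator CT scan form: any haematoma evacuation between the initial and follow-up scans, with type, reason, date and time.
2. In Analysis, state that a volume measured after evacuation is never used as the follow-up volume. Use the last scan taken after randomisation and before evacuation, if one was done clinically. The baseline scan must never fill this role, since it would record zero growth.
3. Where no such scan exists, count evacuation for expansion or deterioration as a progressive haematoma and treat the volume as missing in the main model. With a single follow-up scan, missing values behave much like exclusion and leave some bias, so pre-specify a worst-rank sensitivity analysis alongside.
4. Reword the reason for the existing exclusion: these patients lack an interpretable follow-up volume, not a baseline haematoma.

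The cost is one form item and a few sentences, with no additional scans. The downside is that the substituted scans will be earlier than 24 hours in some patients and may not match the baseline acquisition parameters that the CT scan protocol requires. The number and timing of such scans should be reported by arm.
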